### **13.3. Sample Size Estimation**

#### **13.3.1. Phase 2**

Approximately 171 subjects will be randomized to the Phase 2 part of this study.

Sample size estimation for Cohort 1 (non-ventilated subjects) in Phase 2 is based on the primary efficacy endpoint proportion of subjects alive and free of mechanical ventilation at Day 29, using a Fisher's exact test.

Approximately 120 subjects will be randomized with a 1:1:1 allocation ratio. Assuming the proportion of subjects alive and free of mechanical ventilation at Day 29 is 95% and 75% for the active treatment arm and placebo arm, respectively, 40 subjects per arm will achieve a minimum

80% power for a pairwise comparison versus control when the two-sided alpha value is 0.20, after accounting for 15% drop out.

Sample size for Cohort 2 (ventilated subjects) in Phase 2 is based on the primary efficacy endpoint of mortality rate at Day 29, using the Fisher's exact test. Approximately 51 subjects will be randomized with a 1:1:1 allocation ratio. Assuming the mortality rates at Day 29 are 40% and 80% for the active treatment arm and placebo arm, respectively, 17 subjects per arm will achieve an 80% power for a pairwise comparison versus control when the two-sided alpha value is 0.20.

### **13.3.2. Phase 3**

Approximately 665 subjects will be randomized to the Phase 3 part of this study.

Sample size for Cohort 1 (non-ventilated subjects) of the Phase 3 part is determined based on the primary efficacy endpoint proportion of subjects alive and free of mechanical ventilation at Day 29 (mavrilimumab 6 mg/kg vs placebo), using the Chi square test. The assumptions used for the calculation are adjusted based on the results of Phase 2 portion. Approximately 600 subjects will be randomized with a 1:1:1 allocation ratio. Assuming the proportions for the active arm and placebo arm are 87.5% and 74.4% respectively, approximately 200 subjects per arm are sufficient to achieve at least 90% power for the treatment comparison at the two-sided significance level of 0.05.

Sample size for Cohort 2 (ventilated subjects) of the Phase 3 part is determined based on the mortality rate at Day 29 using a Fisher's exact test. Approximately 117 subjects will be randomized with a 1:1:1 allocation ratio. Assuming the mortality rates for the active arm and placebo arm are 40% and 80% respectively, approximately 39 subjects per arm are required to achieve a 90% power for a pairwise comparison versus control when the two-sided alpha value is 0.025. However, based on review of the Phase 2 Cohort 2 results of the primary and secondary endpoints at day 29, Phase 3 Cohort 2 is closed to further enrollment (approximately 65 subjects randomized at the time of enrollment closure), as there was no evidence that mavrilimumab provided clinical benefit over placebo in recently ventilated patients.

### **13.4. Multiplicity Adjustment**

The cohorts within the Phase 2 and Phase 3 study parts will be analyzed separately unless otherwise specified.

The two-sided type I error rate is 0.2 for each Phase 2 cohort and 0.05 for each Phase 3 cohort. No multiplicity adjustment will be done for the Phase 2 part and Phase 3 Cohort 2 (no formal testing will be done as enrollment for this cohort stopped early).

Multiplicity adjustment for Phase 3 Cohort 1 will be done to guarantee strong control of the overall Type I error rate at a two-sided alpha value of 0.05. For each endpoint, the test statistics for the two comparisons asymptotically follow a bivariate normal distribution and are positively correlated due to sharing a common control arm (placebo). Thus, the conventional Hochberg method will be used to adjust for multiplicity in the analysis of the two dose levels and the sequence of efficacy endpoints. Below are the details.

Considering the hypothesis testing of both the 10 mg/kg and the 6 mg/kg individually versus placebo for each endpoint to be a family, the testing on the primary endpoint and the three ordered secondary endpoints correspond to Family 1, Family 2, Family 3, and Family 4, respectively.

Testing will be done sequentially (Family 1, then 2, 3, and 4) based on the following decision rules (p-values are all two-sided):

- If both p-values in a family are  $\leq 0.05$ , statistically significant treatment effects for the endpoint can be claimed for both dose levels, and testing may proceed to the next family to test those hypotheses at two-sided significance level of 0.05.
- If the larger p-value is  $> 0.05$  and the smaller p-value is  $\leq 0.025$ , a statistically significant treatment effect can be claimed only for the one dose level corresponding to the smaller p-value. Sequential testing stops here, and no further inferential testing can be done. The remaining data analyses will be provided for completeness (with p values as nominal) to inform the discussion of benefit-risk.
- If both p-values in the family are  $> 0.05$ , a statistically significant treatment effect cannot be claimed for either dose level. Sequential testing stops here, and no further inferential testing can be done. The remaining data analyses will be provided for completeness (with p values as nominal) to inform the discussion of benefit-risk.

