### Study Schematic

### Number of subjects (planned):

Phase 2: Approximately 171 subjects

- Cohort 1: Approximately 120 non-ventilated subjects
- Cohort 2: Approximately 51 ventilated subjects

Phase 3: Approximately 665 subjects

- Cohort 1: Approximately 600 non-ventilated subjects
- Cohort 2: Approximately 117 ventilated subjects (approximately 65 subjects at time of enrollment closure)

Based on review of the Phase 2 Cohort 2 results of the primary and secondary endpoints at day 29, Phase 3 Cohort 2 is closed to further enrollment, as there was no evidence that mavrilimumab provided clinical benefit over placebo in recently ventilated patients.

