### 13.2.4. Efficacy Analyses

All efficacy analyses will be based on the mITT for the Phase 2 endpoints and based on the ITT analysis set for the Phase 3 endpoints. Analyses based on other analysis sets will be considered as sensitivity analyses. All efficacy comparisons will be primarily based on each of the mavrilimumab arms versus the placebo arm.

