#### **5.7. Efficacy Analysis**

All efficacy endpoints will be analyzed for the mITT analysis set. The primary and secondary endpoints will also be performed for the Per-protocol analysis set. Treatment comparisons will be for each KPL301 arm vs placebo.

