### **5.7.1. Multiplicity Adjustment**

No multiplicity adjustment will be applied for the Phase 2 part of the study.

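### The Phase 2 type I error of 0.2 is labelled as a cohort rate, but it is the unadjusted level of each of two dose-versus-placebo comparisons

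*Combined protocol and SAP*

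**What the plan says.** Protocol 13.4 (Multiplicity Adjustment), repeated in the synopsis, gives the rates: "The two-sided type I error rate is 0.2 for each Phase 2 cohort and 0.05 for each Phase 3 cohort". The next sentence adds: "No multiplicity adjustment will be done for the Phase 2 part and Phase 3 Cohort 2". The Phase 2 SAP, 5.7.1, agrees: "No multiplicity adjustment will be applied for the Phase 2 part of the study".

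Protocol 13.3.1 shows what 0.20 refers to. Cohort 1 is sized for "80% power for a pairwise comparison versus control when the two-sided alpha value is 0.20, after accounting for 15% drop out", and Cohort 2 is sized on the same per-comparison level. Phase 2 SAP 1.4 uses 0.20 in the same way.

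Each endpoint carries two comparisons. Protocol 13.2.4 says: "All efficacy comparisons will be primarily based on each of the mavrilimumab arms versus the placebo arm". Phase 2 SAP 5.7 says: "Treatment comparisons will be for each KPL301 arm vs placebo". Allocation is equal ("Approximately 120 subjects will be randomized with a 1:1:1 allocation ratio" in Cohort 1, and the same ratio in Cohort 2), so both doses are compared with one placebo arm of the same size.

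The primary endpoints and all other binary endpoints in Phase 2 use Fisher's exact test (Protocol 13.2.4.1 and 13.2.4.2; Phase 2 SAP 5.7.4 and 5.7.5.2). Time-to-event endpoints use a stratified log-rank test (Phase 2 SAP 5.7.5.1).

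**The concern.** A type I error rate stated for a cohort reads as the chance of a false positive somewhere in that cohort. With two unadjusted comparisons at 0.20 each, the design does not provide that.

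The sentence itself encourages the cohort reading. Its second half, 0.05 for each Phase 3 cohort, is meant at cohort level. For Phase 3 Cohort 1 the same section controls the overall rate at 0.05 across both doses by Hochberg. For Phase 3 Cohort 2, Protocol 13.3.2 sized each pairwise comparison at 0.025, which is 0.05 divided by two doses. In Phase 2 the cohort figure and the per-comparison figure are both 0.20, with no division and no combining rule. One phrase therefore carries two meanings.

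What is at stake is how a reader weighs the Phase 2 signal. Protocol 6.1 makes completion of Phase 3 follow from efficacy and safety shown in Phase 2, and 13.3.2 takes the Phase 3 Cohort 1 planning rates from Phase 2. A reader judging that evidence should know whether 0.2 is the false-positive rate of one dose or of the pair.

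**Working it through.** **1. What 0.20 means: reproduce the plan's power.** Exact power of the two-sided Fisher test at alpha 0.20, summing over all 2x2 tables, with the rates in Protocol 13.3.1:

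| Cohort | Rates (active vs placebo) | n per arm | Power | Plan |
|---|---|---|---|---|
| 1 | 95% vs 75% success | 34 (40 x 0.85, i.e. less 15% dropout) | 80.6% | at least 80% |
| 1 | 95% vs 75% success | 40 | 85.7% | – |
| 2 | 40% vs 80% mortality | 17 | 81.4% | 80% |

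The stated power reproduces when 0.20 is the level of one comparison.

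**2. Either-dose rate at nominal size.** With equal arms, the two dose-minus-placebo differences have covariance s²/n and variance 2s²/n each, so their correlation is 0.5. The two-sided 0.20 cut-off is c = 1.2816. With rho = 0.5,

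P(at least one p ≤ 0.20) = 1 − ∫ φ(u) [Φ((c − √rho·u)/√(1 − rho)) − Φ((−c − √rho·u)/√(1 − rho))]² du = 1 − 0.666 = **0.334**.

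Independence would give 1 − 0.8² = 0.36. Counting only false signals of benefit, the rate is 0.168, against 0.10 for one comparison.

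**3. Either-dose rate with the planned Fisher test.** Let all three arms share rate p. For j responders on placebo, let r_j be the chance that one active arm gives a Fisher p-value ≤ 0.20. Given j, the two active arms are independent, so

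rate = Σ_j Bin(j; n, p) · [1 − (1 − r_j)²].

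| Setting | One comparison | Either dose |
|---|---|---|
| Cohort 1, n = 40, 75% success | 0.129 | **0.223** |
| Cohort 1, n = 34, 75% success | 0.124 | 0.215 |
| Cohort 2, n = 17, 80% mortality | 0.087 | **0.155** |
| Maximum over common rates, n = 40 (at 50%) | 0.146 | 0.249 |
| Maximum over common rates, n = 17 (at 50%) | 0.121 | 0.211 |

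Fisher's test is conservative at these sizes, so the attained rate lands near 0.2. That depends on n and on the event rate: Cohort 1 exceeds 0.2 at its own planning rate, and Cohort 2 stays below it at its own.

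**4. What a cohort-level 0.20 would require.** Solving step 2 for 0.20 gives about 0.115 per comparison (Bonferroni: 0.10). At 0.115, Fisher power falls to 71% in Cohort 1 (34 per arm) and 70% in Cohort 2. The Phase 2 sample sizes were therefore not built for a cohort-level 0.20.

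**The case against.** The strongest reply is that nothing is hidden. The next sentence of 13.4 says Phase 2 is unadjusted, 13.3.1 ties 0.20 to a pairwise comparison, and strong control is claimed only for Phase 3 Cohort 1. Unadjusted screening at 0.20 is a legitimate Phase 2 choice. All of that stands. It makes this a mislabelled rate rather than a concealed procedure, but it does not make the label right.

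A second reply is that 0.33 does not describe the primary test. This also stands. With Fisher's test the either-dose rate at the planning placebo rates is 0.223 and 0.155. For false benefit alone it never exceeds 0.125 (40 per arm) or 0.106 (17 per arm) at any common rate from 2% to 98%. The 0.33 figure suits tests near nominal size, such as the log-rank test is expected to be. The size of the stratified log-rank test at 17 to 40 per arm was not checked.

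Stronger readings are tempting, and the documents do not support them:

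- A reader might multiply the error over all the listed endpoints. That needs between-endpoint correlations the documents do not give, and no section states a 0.20 test level for the secondary endpoints. It would also put Fisher-tested endpoints at nominal size.
- A reader might link the inflation to the closing of Phase 3 Cohort 2, which the synopsis describes as "Based on review of the Phase 2 Cohort 2 results of the primary and secondary endpoints at day 29". That cohort was closed for lack of evidence of benefit. Extra false positives make wrongful continuation more likely, so they cannot explain a closure of that kind.
- A reader might treat one dose at p ≤ 0.20 as the trigger for continuing. The documents define no such rule.
- A reader might look for the same error in the Phase 2 SAP. Section 1.4 correctly ties 0.20 to a pairwise comparison, and 5.7.1 states no error rate.

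**Conclusion.** The point holds as a labelling error of minor weight. The 0.2 given for each Phase 2 cohort is the unadjusted two-sided level of each dose-versus-placebo comparison.

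The rate for either dose is not held at 0.20. It is about 0.33 per endpoint for a test at nominal size, which rests on joint normality and the correlation of 0.5 implied by equal arms. For the primary endpoint under Fisher's exact test it is about 0.22 in Cohort 1 and 0.155 in Cohort 2, assuming every arm has the planning placebo rate and the full 40 or 17 subjects. Over common rates it is at most about 0.25 and 0.21.

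No Phase 2 test or sample size is wrong on this account. Phase 3 Cohort 1 is analysed separately with its own control at 0.05, so its alpha is untouched.

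**What to change.** In Protocol 13.4 and the matching synopsis paragraph only, separate the two phases and replace the Phase 2 half of the sentence with wording such as:

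> In Phase 2 each dose-versus-placebo comparison is tested at two-sided 0.20 without multiplicity adjustment; the chance of at least one nominally significant dose when neither works is not held at 0.20 (about 0.33 per endpoint at nominal size; about 0.22 in Cohort 1 and 0.16 in Cohort 2 for the primary endpoint with Fisher's exact test at the planning placebo rates).

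The Phase 2 SAP needs no edit. The cost is wording alone: no subjects, no new test and no loss of power. The stated property becomes less favourable, but it then matches the design. An actual adjustment would be needed only if the sponsor means 0.20 as a cohort-level rate, and it would take Phase 2 power below the planned 80%.

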## **14. DIRECT ACCESS TO SOURCE DATA/DOCUMENTS**

### **14.1. Study Monitoring**

Before an investigational site can enroll a subject into the study, a representative of Kiniksa or designee will contact the investigational study site to:

- Determine the adequacy of the investigational study site and facilities
- Discuss with the Investigator(s) and other personnel their responsibilities with regard to protocol adherence, and the responsibilities of Kiniksa or its representatives. This will be documented in a Clinical Study Agreement between Kiniksa and the Investigator.

During the study, a monitor from Kiniksa or designee will have regular contacts with the investigational site, for the following:

- Provide information and support to the Investigator(s)
- Confirm that facilities remain acceptable
- Confirm that the investigational team is adhering to the protocol, that data are being accurately recorded in the case report forms, and that investigational product accountability checks are being performed
- Perform source data verification
- Record and report any protocol deviations not previously sent to Kiniksa
- Confirm AEs and SAEs have been properly documented on CRFs and confirm any SAEs have been forwarded to Kiniksa and those SAEs that met criteria for reporting have been forwarded to the IRB/EC.

### **14.2. Audits and Inspections**

Authorized representatives of Kiniksa, a regulatory authority, an Independent Ethics Committee or an Institutional Review Board may visit the site to perform audits or inspections, including source data verification. The purpose of a Kiniksa audit or inspection is to systematically and independently examine all study-related activities and documents to determine whether these activities were conducted, and data were recorded, analyzed, and accurately reported according to the protocol, Good Clinical Practice guidelines of the International Conference on Harmonization, and any applicable regulatory requirements. The Investigator should contact Kiniksa immediately if contacted by a regulatory agency about an inspection.

## **15. QUALITY CONTROL AND QUALITY ASSURANCE**

To ensure compliance with Good Clinical Practices and all applicable regulatory requirements, Kiniksa may conduct a quality assurance audit. Please see Section [14.2](#) for more details regarding the audit process.

## **16. ETHICS**

### **16.1. Ethics Review**

Before initiating a trial, the Investigator/Institution must obtain approval/favorable opinion from the IRB or Independent Ethics Committee (IEC) for the trial protocol, written informed consent form, consent form updates, subject recruitment procedures and any other written information to be provided to subjects.

The protocol will be registered in a publicly accessible database such as [clinicaltrials.gov](http://clinicaltrials.gov). In addition, after study completion and finalization of the study report the results of this trial will be submitted for publication and posted in a publicly accessible database of clinical trial results.

This protocol defines the study objectives, the study procedures and the data to be collected on study participants. Additional assessments required to ensure safety of subjects should be administered as deemed necessary on a case-by-case basis. Investigators will apply due diligence to avoid protocol deviations.

The IRB/EC will be informed by the Investigator of any changes to the approved protocol. Any amendments to the protocol will require IRB/IEC approval. Any administrative amendments to the protocol will be provided to IRBs/IECs according to IRB/IEC procedures.

The IRB/IEC will be informed by the Investigator of serious and unexpected SAEs in accordance with the IRB/IEC reporting requirements. The Investigator will provide the IRB/IEC with progress reports per IRB/IEC procedures.

### **16.2. Ethical Conduct of the Study**

This clinical study was designed and shall be implemented, executed, and reported in accordance with the ICH Harmonized Tripartite Guidelines for Good Clinical Practice, with applicable local regulations US CFR 21, and with the ethical principles laid down in the Declaration of Helsinki.

### **16.3. Informed Consent**

Eligible subjects may only be included in the study after providing (witnessed, where required by law or regulation), IRB/EC-approved informed consent.

If applicable, in cases where the subject's representative(s) gives consent (if allowed according to local requirements), the subject must be informed about the study to the extent possible given his/her understanding. If the subject is capable, he/she must indicate agreement by personally signing and dating the written informed consent document.

Informed consent must be obtained before conducting any study-specific procedures (eg, all procedures described in the protocol). The process of obtaining informed consent must be documented in the subject source documents.

Women of child-bearing potential must be informed that taking the study treatment may involve unknown risks to the fetus if pregnancy were to occur during the study and agree that to participate, they must adhere to the contraception requirements specified in this protocol.

A copy of the approved version of all consent forms will be kept by the Investigator.

## **17. DATA HANDLING AND RECORD KEEPING**

The Investigator is responsible for assuring that the data (recorded on CRFs and entered into the eCRF) is complete, accurate, and that entry and updates are performed in a timely manner. The Investigator must certify that the data entered are complete and accurate.

After final database lock, the Investigator will receive copies of the subject data for archiving at the investigational site.

All data should be recorded, handled, and stored in a way that allows its accurate reporting, interpretation, and verification.

### **17.1. Inspection of Records**

The Investigator must maintain source documents for each subject in the study, consisting of case and visit notes (hospital or clinic medical records) containing demographic and medical information, laboratory data, electrocardiograms, and the results of any other tests or assessments. All information on CRFs must be traceable to these source documents in the subject's file. The Investigator must also keep the original informed consent form signed by the subject (a signed copy is given to the subject).

The Investigator must give the monitor access to all relevant source documents to confirm their consistency with the data capture and/or data entry. Additional checks of the consistency of the source data with the CRFs are performed according to the study-specific monitoring plan. No information in source documents about the identity of the subjects will be disclosed.

### **17.2. Retention of Records**

The Principal Investigator must maintain all documentation relating to the study for a period of 2 years after the last marketing application approval, or if not approved 2 years following the discontinuance of the test article for investigation. If it becomes necessary for Kiniksa or the Regulatory Authority to review any documentation relating to the study, the Investigator must permit access to such records.

## **18. PUBLICATION POLICY**

Publication of the study results shall be done in accordance with, and are subject to, the publication provision in the clinical trial agreement governing this study.

## 20. SUMMARY OF CHANGES

### 20.1. Changes from Global Protocol Version 5 (Amendment 4) to Global Protocol Version 6 (Amendment 5)

The following are changes to the KPL-301-C203 protocol (Global version 5: 14Jun2021), which summarizes major changes to the protocol. Additional minor changes were also made with respect to use of abbreviations, correction of typos, renumbering of sections (when necessary), and revising/formatting references. The table of contents was updated.

Protocol Section (Page Number  )	Modification	Rationale
Emergency Contact Information (p4)	Updated Drug Safety Physician from [REDACTED]	Administrative update
Synopsis (p7-8) and Section 10.2 (p48)	
Secondary Endpoints:
 
Secondary efficacy endpoints will be examined based on the hierarchical order <del>specified in the multiplicity adjustment section below:</del>
 
Cohort 2 (Ventilated Subjects)
 
 
Time to 1-point clinical improvement by Day 29
 
 
Defined as time from randomization to a 1-point improvement on the NIAID 8-point ordinal scale, or discharge from the hospital, whichever occurs first. Subjects who die before Day 29 will be censored at Day <del>30</del> 35.
	
Unnecessary text.
 
Censoring of time to event endpoints revised to incorporate day 29 visit window (+4 days) and 1 day for difference between randomization and dosing

Synopsis (p8) and Section 10.3 (p48)	[REDACTED]	[REDACTED]

 Page number for the tracked change version.

